6.7 BASELINE, TIME WINDOWS AND CALCULATED VISITS

Definition of baseline

In general, baseline is defined as the last non-missing measurement on or prior to the first administration of study medication. In the case that the first dose of study medication is delayed beyond the date of randomisation, a post-randomisation value can be used as a baseline value provided that it meets the stated requirement.

Where clock times are available (expected to include laboratory safety data, 12-lead ECG, plasma BI 456906 concentrations and biomarkers) they will be used in addition to dates to define baseline, since it is also expected that the time of first study drug administration will be accurately recorded on the eCRF for all patients.

For vital signs, the baseline definition will make the additional requirement that the data records are pre-dose. In practice, this will also be done using the clock times as well as the date. Three pre-dose measurements are expected to be captured at the baseline visit (Visit 2); the mean of these 3 measurements (or the mean of the available measurements if fewer) will be used as baseline. In any situation in which only post-dose measurements are available at Visit 2 and no pre-dose measurements, Visit 2 will not be used as baseline; the mean of the 3 measurements (or those available if fewer) at the screening visit (Visit 1) will be used as baseline instead.

Unscheduled and repeat assessments (where available and relevant) are eligible for use as baseline values provided that they meet the above criterion.

Visit windows

All summaries and analysis which are presented by week will use a visit window to classify the data record, which is derived from the assessment date relative to a reference date, taken here to be the date of first administration of study medication. This approach allows appropriate classification of visits which may have occurred significantly earlier or later than the protocol assessment schedule, as well as the use of data captured at visits which have no fixed timing (notably the EOT visit). Relative day will be defined for this purpose as *(date of assessment – date of first administration of study medication) + 1*.

Nominal database visit labels will not be used in any summary or analysis by time point, unless otherwise stated.

Prior to applying the visit windows specified below, it will first be determined whether the data record is on-treatment, as defined in [Section 6.1.6](#), for summaries or analysis which require this approach.

Unscheduled and repeat assessments (where relevant/available) are eligible for inclusion in visit windows.

For all variables except 12-lead ECG, if a patient has more than one non-missing value within the same visit window, the value closest to the target day will be selected. If two non-missing values are the same distance from the target day, the earlier of the two values will be selected.

For 12-lead ECG (only), scheduled visits take precedence over unscheduled visits. Once this rule has been applied, the measurement closest to the target day will be used. If there are two observations which have the same difference in days to the planned day (but are not on the same day), the later of the two values will be selected.

Derivation of last, minimum and maximum values where relevant in safety analyses will consider all available values, regardless of whether they were selected in the visit window.

The derivation of the maximum value of an ECG interval (or worst case of the morphological assessment, if applicable) will consider all on-treatment values (whether or not selected in any time window; see [Section 6.1.6](#) for definition of on-treatment).

Two different situations are envisaged, which are described in the following tables:

- Visit windows for variables scheduled to be assessed at all or many visits
- Visit windows for variables with a sparse visit schedule.

Table 6.7: 1 Visit windows for variables scheduled to be assessed at all or many visits

Period	Time Point	Target Day	Visit Window
Dose escalation	Week 2	15	2-21
	Week 4	29	22-35
	Week 6	43	36-49
	Week 8	57	50-63
	Week 10	71	64-77
	Week 12	85	78-91
	Week 14	99	92-105
	Week 16	113	106-119
	Week 18	127	120-133
Maintenance	Week 20	141	134-154
	Week 24	169	155-182
	Week 28	197	183-210
	Week 32	225	211-238
	Week 36	253	239-266
	Week 40	281	267-301
	Week 46	323	≥ 302

The relevant variables are expected to include body weight measured at the clinic and BMI derived from this, vital signs, routine non-fasting laboratory safety variables, 12-lead ECG and the mental health questionnaires (C-SSRS, PHQ-9).

These visits windows will also be used for waist circumference, although this is not scheduled to be captured at all weeks displayed.

Table 6.7: 2 Visit windows for variables with a sparse visit schedule

Period	Time Point	Target Day	Visit Window
Dose Escalation	Week 10	71	2-133
Maintenance	Week 20	141	134-231
	Week 46	323	≥ 232

The relevant variables are expected to include biomarkers, HbA1c, fasting laboratory variables, PRO questionnaires, the 3-day food diary and the obesity staging questionnaires (EOSS and CDMS).

The suitability of these visit windows for very sparse data capture will be reviewed at the Report Planning Meetings (RPMs).

Vital signs

For vital signs, the following windowing rules will be applied within each visit to determine pre-dose, 15 minutes post-dose (selected visits only) and 60 minutes post-dose from recorded clock times:

- If the vital signs measurement time is prior to or equal to the time of study drug administration, then it is considered eligible for pre-dose, without restriction on how long before study drug administration the measurement was done (provided it was still done on the same visit date). The mean of the 3 values (or those available if fewer) will be used as pre-dose. If more than 3 pre-dose values are identified in this way, the mean of the 3 values closest to the time of study drug administration will be used.
- If the vital signs measurement time is after the time of study drug administration, then it is considered eligible for post-dose, without restriction on how long after study drug administration the measurement was done (provided it was still done on the same visit date).
 - For visits where only one post-dose time point is scheduled, then all post-dose records will be considered eligible for 60 minutes post-dose. The mean of the 3 values (or those available if fewer) will be used as 60 minutes post-dose. If more than 3 values are identified in this way, the mean of the 3 values closest to the target 60 minute time point will be used.
 - For visits where two post-dose time points are scheduled, then measurements will be considered eligible for 15 minutes post-dose if they were done on or before 37.5 minutes after study drug administration, and eligible for 60 minutes post-dose if they were done later than this. In both cases, the mean of the 3 values (or those available if fewer) will be used. If more than 3 values are identified in this way, the mean of the 3 values closest to the target 15 minute or 60 minute time point will be used, respectively.

The situation in which vital signs measurement time is exactly equal to the time of study drug administration is not clinically plausible, and a rule for handling it is included above only for completeness, in case this cannot be resolved for any patients and this situation remains on the database at DBL.

Any vital signs record for which no time of study drug administration exists (expected to include measurements recorded during the 28 day REP and scheduled Week 46 measurements) will be considered “pre-dose” according to the above rules. Only pre-dose measurements will be used for efficacy purposes (blood pressure endpoints).

Home-measured body weight

Home-measured body weight will be classified into weeks using the available dates recorded by the patient in the eDiary, and using a strict definition of each week relative to the date of first administration of study medication. In other words. “Week 1” will be defined as Day 2-8, “Week 2” will be defined as Day 9-15, “Week 3” will be defined as Day 16-22, etc.

If a patient has more than one non-missing value within the same week, the mean of all available values will be used.

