5.2.2 Vital signs

Vital signs will be evaluated at the time points specified in the [flowchart](#), prior to blood sampling.

This includes temperature, respiratory rate, systolic and diastolic blood pressure and pulse rate (electronically or by palpation count for 1 minute) in a seated position after 5 minutes of rest. The results must be included in the source documents available at the site. At dosing visits vital signs evaluations will be performed pre-dose and within 60 min after the end of drug administration and at Visit 2 (1st dosing visit) and Visit 3 (2nd dosing visit) additional measurements will be performed approximately 15 minutes post-dose (15 min. after last injection) and approximately 60 minutes post-dose (60 min. after last injection). Further details on the procedure for blood pressure measurements are given in [appendix 10.2](#)

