7.8.3 Vital signs

Descriptive statistics will be presented over time for absolute values and changes from baseline in each of the vital signs variables.

The time points to be presented will follow the expected data structure for each vital signs variable as follows:

- For systolic and diastolic BP, three measurements are planned to be captured at each of pre-dose (all weeks), 15 minutes post-dose (selected weeks only) and 60 minutes post-dose (all weeks). The descriptive summary will therefore display all relevant time points within week. Multiple measurements at each time point will be handled using the rules in [Section 6.7](#).
- For pulse rate, one measurement is planned to be captured at each of pre-dose (all weeks), 15 minutes post-dose (selected weeks only) and 60 minutes post-dose (all weeks). The descriptive summary will therefore also display all relevant time points within week.
- For respiratory rate and temperature, a single measurement is expected to be captured at each week. The descriptive summary will therefore not display a time point within week.

Body weight and waist circumference over time are covered entirely within the relevant efficacy sections, and are not considered further as part of safety.

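### SAP Table 6.7:1 has no Day 1 (Week 0) row, so the 15- and 60-minute vital signs after the first injection fall in no time point of the by-week safety summaries that SAP 7.8.3 plans

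*SAP*

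**What the plan says.** **Collection.** Protocol 5.2.2 requires vital signs before and after dosing at each dosing visit and adds, for two visits only, that "at Visit 2 (1st dosing visit) and Visit 3 (2nd dosing visit) additional measurements will be performed approximately 15 minutes post-dose", with a further set at about 60 minutes. The flow chart puts Visit 2 on Day 1 and Visit 3 on Day 15 (Week 2).

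**Classification.** SAP 6.7 states that "All summaries and analysis which are presented by week will use a visit window to classify the data record". Relative day is the assessment date minus the date of first dose, plus 1. The section adds that "Nominal database visit labels will not be used in any summary or analysis by time point, unless otherwise stated". Vital signs are named among the variables that use Table 6.7:1, whose first row is Week 2, target Day 15, window Days 2 to 21.

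**Baseline.** The SAP says "For vital signs, the baseline definition will make the additional requirement that the data records are pre-dose". If Visit 2 has only post-dose readings, baseline goes back to the screening visit.

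**Within-visit labels.** SAP 6.7 also uses clock times to label readings as pre-dose, 15 minutes or 60 minutes. At visits with two post-dose time points the cut is 37.5 minutes.

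**Display.** SAP 7.8.3 plans descriptive statistics over time, as values and changes from baseline. For blood pressure and pulse it lists a pre-dose reading at every week, a 15-minute reading at certain weeks and a 60-minute reading at every week, and concludes: "The descriptive summary will therefore display all relevant time points within week".

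**The concern.** A record needs two labels to appear in the 7.8.3 tables: a week, from the date window, and a time within that week, from the clock. The Visit 2 post-dose readings receive the second label but not the first. They are the only scheduled vital signs taken after the first injection, and they are on-treatment under SAP 6.1.6, so a reader of 7.8.3 would expect to see them.

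Visit 3 does not stand in for them. Under protocol Table 4.1.4:1 every active arm is at 0.3 mg in treatment weeks 1 and 2 and at 0.6 mg from week 3, so with weekly injections Visit 3 is about the third injection and at a different dose. The ECG does not fill the gap either, because protocol 5.2.4 has it recorded before dosing. What is at stake is whether the report shows first-injection post-dose blood pressure and pulse by treatment group at all.

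**Working it through.** This is a check of rules. The only arithmetic is the day count and a count of readings.

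**1. The SAP's own target days.** With first dose on Day 1, the target day is 7 × week + 1. Week 2 gives 7 × 2 + 1 = 15 and Week 46 gives 7 × 46 + 1 = 323. All 16 target days in Table 6.7:1 reproduce.

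**2. Coverage.** The windows run without a gap from Day 2 (Week 2, Days 2 to 21) to Day 301 (end of Week 40), and Week 46 takes Day 302 onward.

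**3. Relative day of the readings.** A reading taken minutes after the first injection has the same date as that injection: 0 + 1 = Day 1. This holds even if the first dose is delayed after randomisation, because the reference date is the first-dose date.

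**4. Where each record goes.**

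| Record | Relative day | Baseline? | Table 6.7:1 window |
|---|---|---|---|
| Visit 2, pre-dose | 1 | Yes | Not needed |
| Visit 2, 15 min post-dose | 1 | No (post-dose) | None |
| Visit 2, 60 min post-dose | 1 | No (post-dose) | None |
| Visit 3, 15 and 60 min post-dose | 15 | No | Week 2 |

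Table 6.7:2, for sparsely scheduled variables, also starts at Day 2 and would not catch them.

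**5. Could another rule pick them up?**
- The clock-time rule assigns a time within a visit and no week.
- SAP 6.7 lets last, minimum and maximum values ignore the windows where such values are relevant. SAP 7.8.2 plans those displays for laboratory data; 7.8.3 plans none for vital signs.
- The bar on nominal labels allows stated exceptions. Neither 6.7 nor 7.8.3 states one for Visit 2.

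**6. Comparison with the display plan.** SAP 7.8.3 speaks of 15-minute readings at weeks, in the plural. The protocol schedules them at two visits. Only one of the two (1/2 = 50%) has a window.

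**7. Size.** Assume all 350 planned patients are dosed and fully measured. Blood pressure: 350 × 2 time points × 3 repeats = 2,100 readings, which reduce after averaging to 350 × 2 = 700 patient-level means each for systolic and diastolic pressure. Pulse: 350 × 2 × 1 = 700 readings.

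**The case against.** The best reply is that the SAP evidently means to show these readings. Table 6.1.1:1 already calls Visit 2 Week 0, the baseline paragraph foresees post-dose records at Visit 2, the clock-time rule has a branch for visits with two post-dose times, and 7.8.3 promises every relevant time within week. Table 6.7:1 also has no row for baseline, which is nevertheless used, so absence from the table need not mean absence from the output. A programmer might well add a Week 0 column unprompted.

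This stands as evidence of intent, and it rules out one inference a reader might draw: that the SAP made a deliberate analysis choice to leave the readings out. It does not close the gap. Baseline needs no row because it has its own definition; the Day 1 post-dose readings have neither. An unprompted column would rest on a visit label that 6.7 says not to use.

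It is also fair that the consequence is modest. Vital-sign output is descriptive, all active arms are at the same dose on Day 1, so the readings carry no comparison between doses, and Visit 3 repeats both time points.

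Finally, some SAP sections are not in the public text and might deal with Visit 2. That cannot be checked, but 7.8.3 refers only to 6.7 for the handling of these measurements.

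**Conclusion.** The point holds as an inconsistency within the SAP. Followed literally, 6.7 omits from the by-week safety summaries two post-dose time points at Visit 2 for systolic pressure, diastolic pressure and pulse, and leaves the 15-minute summary with Week 2 alone, against what 7.8.3 plans. It is worth correcting but affects descriptive safety tables only. It rests on the visible SAP text containing the whole rule.

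Three stronger readings are not supported:
- *The data are lost.* They stay in the database, and protocol 5.2.6.1.1 has vital-sign changes judged clinically relevant recorded as adverse events, which are summarised.
- *The extra readings exist to capture the cardiovascular response to first exposure, and the plan defeats that aim.* Protocol 5.2.2 gives no reason for them, and the cardiac entry in the 1.4.2 risk table names ECG monitoring.
- *Efficacy results are affected.* The blood pressure endpoints use only pre-dose readings or readings at visits without dosing.

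**What to change.** Add one row to Table 6.7:1, marked as applying to vital signs only: **Week 0 (first dose), target Day 1, window Day 1, post-dose records only**, with 15- and 60-minute time points. The existing 7.8.3 rule then covers the summary, as value and change from the pre-dose baseline; a cross-reference there to the new row would remove doubt. Limiting the row to post-dose records keeps the pre-dose baseline from being counted twice.

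The cost is one extra time point in the descriptive tables. The data are already scheduled for collection, and no endpoint, test or other window changes.

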5.2.5.4 Mental health questionnaires

The mental health status of subjects will be assessed by C-SSRS and PHQ-9 questionnaires.

The C-SSRS is a semi-structured, investigator-rated interview, developed by clinical experts in cooperation with the FDA, assessing both suicidal behaviour and suicidal ideation. It does not give a global score but provides some categorical and some severity information specifically for behaviour and ideation.

The C-SSRS interview may be administered by any type of physician, psychologist, clinical social worker, mental health counsellor, nurse, or research coordinator with C-SSRS training. It has a typical duration of five minutes and causes only a low burden on patients. At a minimum, the interview consists of 2 screening questions related to suicidal ideation and 4 related to suicidal behaviour and may be expanded to up to 17 items in case of positive responses.

The C-SSRS has been widely used in large multinational clinical trials. The C-SSRS will be administered at the screening visit (using the “baseline/screening” version) with the aim to exclude subjects with a lifetime history of suicidal ideation and behaviour. After the baseline visit, the assessment “since last visit” will be performed at clinic visits as specified in the [Flow Chart](#). The investigator is to review positive and negative reports for plausibility and

clinical relevance. Doubtful reports may be repeated, or reports may be validated by a consulting psychiatrist. If there is a positive report of suicidal behaviour or suicidal ideation type 4 or 5 after start of trial, the investigator is to immediately interview the patient during the clinic visit and advise the patient to consult with a psychiatrist. If the positive report is confirmed, appropriate actions for the patient's safety must be initiated. Treatment with study drug should be stopped and patient should be discontinued from the trial. Additionally, all C-SSRS reports of suicidal ideation type 4 or 5 and all reports of suicidal behaviour must be reported as separate SAEs by the investigator. For 'Self-injurious behaviour, no suicidal intent' (Type 11) standard AE / SAE reporting rules are to be applied. For each negative report (suicidal ideation type 1, 2 or 3) after start of the trial, the investigator is to decide based on clinical judgment whether it represents an AE as defined in the protocol, and if it is considered an AE then it must be reported accordingly.

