7.8.5 Others

Frequency tables will be produced of the information in both the C-SSRS and PHQ-9 questionnaires over time.

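### The by-week C-SSRS and PHQ-9 tables keep one record per visit window, so type 1 to 3 ideation or a raised PHQ-9 score can be missing from every planned summary

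*SAP*

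**What the plan says.** SAP 6.7 classifies records into weeks by date. The variables assigned to the dense windows of Table 6.7:1 include "12-lead ECG and the mental health questionnaires (C-SSRS, PHQ-9". For everything except ECG, "if a patient has more than one non-missing value within the same visit window, the value closest to the target day will be selected", and on a tie the earlier record is kept.

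Extra records are allowed in: "Unscheduled and repeat assessments (where relevant/available) are eligible for inclusion in visit windows". Windowing by date is also justified "as well as the use of data captured at visits which have no fixed timing (notably the EOT visit".

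The only planned display of the two instruments is in SAP 7.8.5: "Frequency tables will be produced of the information in both the C-SSRS and PHQ-9 questionnaires over time".

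Protocol 5.2.5.4 sets the recall period of the C-SSRS after baseline: "the assessment “since last visit” will be performed at clinic visits". The same section requires every report of type 4 or 5 ideation and every report of suicidal behaviour to be filed as a separate serious adverse event. Ideation of types 1 to 3 is an adverse event only if the investigator judges it so. No adverse event rule is stated for PHQ-9 scores.

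**The concern.** Closest-to-target selection suits a point measurement such as body weight, where two values a few days apart estimate much the same thing. A C-SSRS record is a report on an interval. Two records in one window cover two different intervals, and the next record starts where the dropped one ended, so nothing later need repeat what was dropped. The by-week table can then show a patient without ideation in a window in which ideation was reported.

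For PHQ-9 the recall argument does not apply, since the protocol describes no such form of it. The gap there is simpler: no maximum post-baseline score is planned, so a high score that is not the selected one is not displayed.

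Suicide risk, depression and mood disorder are listed trial risks in Protocol Table 1.4.2:1, with the C-SSRS as the mitigation. These tables are the only instrument-based summary of that risk in the public text.

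**Working it through.** The plan gives no figure to reproduce. The check applies the stated rules to the nominal calendar.

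**Inputs**
- Windows and targets: SAP Table 6.7:1 (Week 24: target 169, days 155-182; Week 46: target 323, day 302 onwards). All 16 targets equal 7 × week + 1.
- On-treatment: up to last dose + 28 days inclusive (SAP 6.1.6). Safety analyses use on-treatment data only (SAP 7.8), and this filter is applied before windowing (SAP 6.7).
- Weekly dosing, last planned dose on day 316; EOT 7 days after the last dose and follow-up 3 weeks later (Protocol flow chart footnotes). Protocol 6.1 makes 28 days after the last dose the minimum for follow-up.
- Assumed: C-SSRS and PHQ-9 at each scheduled visit on its target day, at EOT and at follow-up, and not at later weight-only visits. The public flow chart text does not show the C-SSRS row after Visit 11; Table 1.4.2:1 says the scale is applied at every visit.

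**Unscheduled visit.** Scheduled Week 24 visit on day 169 with no ideation; unscheduled visit on day 175 with ideation. Both fall in 155-182. The distances to target are 0 and 175 − 169 = 6, so day 169 is kept. The Week 28 interview on day 197 looks back only to day 175, so days 169 to 175 are described by no displayed record. In general, an on-target scheduled record beats any other record in its window: from day 2 to day 344 there are 343 days, less 16 target days, which leaves 327 days on which an unscheduled record would lose. If the scheduled record is missing or further from target, the unscheduled one is kept.

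**EOT after early discontinuation.** Possible last-dose days before day 316 are 1, 8, ..., 309, which is 45 days: 20 in escalation (1 to 134) and 25 in maintenance (141 to 309).
- Escalation: with visits every two weeks, an EOT visit 7 days after a scheduled visit falls on the first day of the next window (last dose day 29, EOT day 36, window 36-49). None of the 20 is lost.
- Maintenance, lost to the scheduled record: last-dose days 141, 169, 197, 225, 253, 281 and 288. For example, last dose day 169 gives EOT day 176, in window 155-182, with distances 7 against 0. That is 7 of 25.
- Maintenance, follow-up at exactly +28 days: the follow-up record is still on-treatment and can also beat the EOT record. Last dose day 148 gives EOT day 155 (distance 14) and follow-up day 176 (distance 7). This adds last-dose days 148, 176, 204, 232, 260, 295 and 302, giving 14 of 25.

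**Completers.** EOT is combined with Visit 19 on day 323 and is kept. Follow-up on day 344 is on-treatment (316 + 28 = 344), falls in the Week 46 window and loses by 344 − 323 = 21 days against 0. From day 345 it is off-treatment and is excluded before windowing.

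**Rescue rules.** SAP 6.7 says "Derivation of last, minimum and maximum values where relevant in safety analyses will consider all available values", but only where relevant. SAP 7.8.2 uses this by tabulating last, minimum and maximum laboratory values. ECG has its own rule: the maximum ("or worst case of the morphological assessment, if applicable) will consider all on-treatment values"). SAP 7.8.5 names no such summary for C-SSRS or PHQ-9, and the C-SSRS has no global score to which a maximum would naturally apply.

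**The case against.** The strongest reply is that the serious signal is not lost. Protocol 5.2.5.4 reserves the word positive for type 4 or 5 ideation and behaviour, and all of these must be serious adverse events. SAP 7.8.1 counts adverse events by patient without visit windows. This stands. A reader might infer that suicidality can vanish from the trial's safety reporting, and the documents do not support that.

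A reader might also count calendar days and conclude that about half of EOT records after an on-target visit are lost: 13 of the 27 days between four-weekly visits, or 6 of the 13 between two-weekly visits. That ignores weekly dosing with EOT seven days after the last dose. Between days 169 and 197 the nominal EOT days are 176, 183 and 190, and only 176 loses to the scheduled visit. Between days 29 and 43 the only one is day 36, and it is kept.

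Nor does the selection rule explain most follow-up losses, since records after last dose + 28 days go under the on-treatment rule. Unscheduled C-SSRS records may also be few, because procedures at such visits are left to the investigator (Protocol 6.2.2), and nothing in the documents supports a sizeable selective effect. Finally, SAP section 5.4 is not in the public text and may hold further derivations.

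These points limit how often records are lost and how serious the lost ones are. They do not remove the gap, because the clause on last, minimum and maximum values is attached to no planned C-SSRS or PHQ-9 table.

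**Conclusion.** The concern holds in limited form. Followed as written, the SAP can display a patient without ideation in a window in which ideation was reported. What can be absent from every summary in the public text is type 1 to 3 ideation not judged an adverse event, and raised PHQ-9 scores. For type 4 or 5 ideation and behaviour the event reaches the adverse event tables, although its C-SSRS category may be missing from the C-SSRS table.

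The sizes above count nominal last-dose days, not patients, and rest on collection at EOT and follow-up. They also rest on exact timing. An EOT visit one day early in escalation (day 35 after a last dose on day 29) would fall in window 22-35 and lose to day 29. A C-SSRS at the Week 46 visit of patients who stop late would add losses. The tables are descriptive, and no efficacy result is affected.

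**What to change.** Add to SAP 7.8.5:

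1. A table of patients with any on-treatment post-baseline occurrence of each C-SSRS ideation type and each behaviour category.
2. A summary of the maximum on-treatment post-baseline PHQ-9 score.

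Both should use all on-treatment records, scheduled, unscheduled, EOT or follow-up, whether or not a window selected them, as SAP 6.7 already does for ECG. Records more than 28 days after the last dose should be shown separately as follow-up, which keeps to the on-treatment default of SAP 7.8. Because Protocol 5.2.5.4 lets doubtful reports be repeated, a footnote should say how a repeated report is counted. The by-week tables can stay as they are.

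The cost is SAP wording and one or two tables from data already collected. With these tables, losses of on-treatment records to window selection fall to zero. The downside is small: patients with extra visits have slightly more chances to be counted as positive.
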